5.2.4 Vital Signs Data

Descriptive statistics will be provided by treatment group, for both vital signs and change from baseline in vital signs. The incidence of treatment-emergent potentially clinically significant vital sign results will also be summarized by treatment groups. Listings of potentially clinically significant abnormalities will also be provided.

For a subject with repeat measures in either vital signs or laboratory tests at a visit, the last repeat will be used in the by visit summary. However, for outlier analysis (such as clinically significant abnormalities), data from all visits, no matter they are from the original visits, repeats, or unscheduled visits, will be included.

5.2.5 Electrocardiogram Data

Electrocardiogram (ECG) data will not be summarized since ECG data will be collected at the screening visit only.

5.2.6 Postbaseline Concomitant Medications

Concomitant medications used postbaseline will be summarized in two categories of time interval: during the IMP period and after the IMP period. In each case, the use of concomitant medications will be summarized by number and percentage of users by treatment group.

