3.1 Treatment Phase A

All subjects will initially receive tolvaptan once daily on Days 1 and 2. If a subject's serum sodium level has not increased by at least 4 mEq/L (mmol/L) by end of Day 2, an additional day of treatment is required and is referred to as Day 2a. If subjects do not achieve an increase in serum sodium concentration of ≥ 4 mEq/L (mmol/L) on Day 2a, they will be defined as nonresponders. If subjects achieve an increase in serum sodium concentration of ≥ 4 mEq/L (mmol/L) on end of Day 2 (or 2a), they will be defined as responders.

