3.2 Treatment Phase B

On Day 3, responders will be randomized to either the Early Withdrawal group or the Late Withdrawal group. Subjects in the Late Withdrawal group continue tolvaptan treatment on Days 3 and 4, subjects in the Early Withdrawal group do not receive additional tolvaptan treatment on Days 3 and 4. Nonresponders will not be randomized.

For nonresponders from Treatment Phase A, the investigator will determine if the subject is to either:

- Continue treatment with IMP for Days 3 and 4, or
- Prescribe treatment per local standard of care for Days 3 and 4.

Randomization will be stratified by age [REDACTED], serum sodium response [REDACTED], and underlying hyponatremia etiology [REDACTED]
[REDACTED]

Subjects randomized to the Early Withdrawal group will be observed to determine whether additional intervention is required to maintain appropriate serum sodium levels. Subjects whose serum sodium declines by ≥ 4 mEq/L (mmol/L) or whose overall clinical condition requires further treatment to raise serum sodium levels should be treated per local standard of care. Any intervention intended to raise serum sodium concentration during the first 48 hours of Treatment Phase B (including fluid restriction) will be defined as rescue therapy. Subjects receiving rescue therapy will be considered to have reached their clinical endpoint, and their data will be censored from that time forward.

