5.1.5 Treatment Compliance

Treatment compliance will be calculated by dividing the total dose taken by the total dose the subjects are scheduled to take during the trial. For the Early Withdrawal subjects, the subjects are not scheduled to take the IMP in Treatment Phase B, the compliance will be 100% for these subjects unless they accidentally take the IMP.

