5.2 Safety Analysis

The safety analysis will be conducted based on the Safety Samples, which are defined in [Section 5.1.1](#). Safety variables to be analyzed include adverse events (AEs), clinical laboratory data, and vital signs. In general, summary statistics will be provided for safety variables based on all available data.

Safety analyses will be performed for Treatment Phase A and Treatment Phase B separately. Safety analyses by age categories [REDACTED]
[REDACTED] will be provided as well.

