5.2.1 Duration of Exposure to Trial Medication

Duration of exposure to each treatment of each subject will be summarized by treatment group. A subject's duration of exposure is defined as the IMP end date – IMP start date + 1.

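### The concomitant-medication table in SAP 5.2.6 puts randomized Phase B in different columns for the two arms, so non-rescue co-treatment is not summarized on a common window

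*SAP*

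**What the plan says.** SAP 5.2.6 sets two windows: "Concomitant medications used postbaseline will be summarized in two categories of time interval: during the IMP period and after the IMP period". It continues: "In each case, the use of concomitant medications will be summarized by number and percentage of users by treatment group". The term IMP period is not defined. The nearest definition is in SAP 5.2.1: "A subject's duration of exposure is defined as the IMP end date", minus the start date, plus one.

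The dosing schedule is in SAP 3.1 and 3.2. In Phase A, "All subjects will initially receive tolvaptan once daily on Days 1 and 2", with a further Day 2a for those who have not yet responded. In Phase B, "Subjects in the Late Withdrawal group continue tolvaptan treatment on Days 3 and 4", whereas "subjects in the Early Withdrawal group do not receive additional tolvaptan treatment on Days 3 and 4". SAP 5.1.5 repeats this for Early Withdrawal: "the subjects are not scheduled to take the IMP in Treatment Phase B".

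The parent section, SAP 5.2, has a general rule: "Safety analyses will be performed for Treatment Phase A and Treatment Phase B separately". Its list of safety variables names adverse events, laboratory data and vital signs, but not concomitant medications.

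**The concern.** Phase B is the only part of the trial in which the groups differ by randomization. A by-arm medication table is useful there if both arms are observed over the same days. Windows tied to each subject's own dosing do not give that, because the randomized assignment itself decides when dosing ends. The during column then sets Phase A in one arm against Phases A and B in the other. The after column sets Phases B and C against Phase C alone.

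The trial is open-label, so the treating team knows who has stopped tolvaptan. Some co-treatments can affect sodium or fluid balance without being given to raise sodium, and so fall outside the rescue definition. Examples are steady-dose diuretics (Protocol 3.3.1.2) and hypotonic IV saline for fluid management (Protocol 4.2). A reader who wants to know whether such treatment was balanced between arms during Phase B would look to 5.2.6 and not find the answer in the table as specified.

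**Working it through.** There is no stated figure to reproduce; the check is a count of days.

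**Inputs.** Phase A dosing days: 2, or 3 with Day 2a (SAP 3.1). Phase B dosing days: 2 for Late Withdrawal, 0 for Early Withdrawal (SAP 3.2). The during window is taken as first to last dose, following SAP 5.2.1. The after window is taken as the 14 days following the last dose, up to the nominal final contact (SAP 3.3). Days are numbered consecutively, so with Day 2a the two Phase B days become days 4 and 5.

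| Phase A days | Arm | During | After | Phase B days in during | Phase B days in after |
|---|---|---|---|---|---|
| 2 | Early | 1–2 | 3–16 | 0 of 2 | 2 of 2 |
| 2 | Late | 1–4 | 5–18 | 2 of 2 | 0 of 2 |
| 3 | Early | 1–3 | 4–17 | 0 of 2 | 2 of 2 |
| 3 | Late | 1–5 | 6–19 | 2 of 2 | 0 of 2 |

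The during window is two days longer in Late Withdrawal. The after windows are equally long, but only the Early Withdrawal one contains Phase B.

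**Rescued Late Withdrawal subjects.** Protocol 3.2.4.2 takes a rescued subject off trial treatment. If that happens after the Day 3 dose, the last dose is on Day 3, and Day 4 moves to the after column. That subject contributes 1 of 2 Phase B days to each column. The split within this arm therefore depends partly on outcome.

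**A common window already exists.** SAP 5.1.7.2 ends Phase B at 72 hours after the last dose for Early Withdrawal and at the 24-hour trough of Day 4 for Late Withdrawal. Without Day 2a, Day 2 + 72 hours and Day 4 + 24 hours both fall on Day 5. Randomization to end of Phase B is thus the same nominal interval in both arms.

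**Illustrative size.** Suppose a drug has the same chance p of use each day in both arms, independently across days. The chance of at least one use in d days is 1 − (1 − p)^d.

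- p = 0.10: 1 − 0.9² = 19% against 1 − 0.9⁴ = 34%. With Day 2a, 1 − 0.9³ = 27% against 1 − 0.9⁵ = 41%.
- p = 0.05, two against four days: 10% against 19%.
- p = 0.20, two against four days: 36% against 59%.

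These are differences in the during column with no true difference in use. The values of p are assumptions. Independence matters as much: a drug started in Phase A and continued throughout counts once in the during column of each arm, and the artefact is zero. A drug given only on the two Phase B days appears solely in the after column for Early Withdrawal and solely in the during column for Late Withdrawal completers.

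**The case against.** A reader might infer that co-treatment cannot be compared between the arms at all, that 5.2.6 is the only place where sodium-active treatment would be seen, or that the primary comparison is left exposed. The documents do not support any of these.

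- Concomitant medications are recorded at every visit in both arms (Protocol, Table 3.7-1). A Phase B table is unspecified, not impossible.
- SAP 5.1.8.2 summarizes rescue therapy and fluid restriction for Phases A and B, and SAP 5.1.7.2 defines rescue broadly, to include any treatment meant to raise sodium. SAP 5.1.6 also tabulates major protocol deviations, including those in concomitant medication, by center and treatment group. What is left for 5.2.6 is treatment given for other reasons. One limit stands: 5.1.8.2 does not say that its percentages are by randomized group.
- SAP 5.1.7.1 censors data after rescue in the primary analysis. SAP 5.1 reduces efficacy to summary statistics because of low enrollment and early termination. No primary test is planned that an imbalance could distort, although that sentence does not waive 5.2.6.

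Two objections go to the reading itself. First, the allocation follows from a natural reading of an undefined term. Protocol 3.10 describes a treatment period that covers evaluation for the objectives whether or not all doses were taken, and that would include Phase B in both arms. But the term is different, and SAP 5.2.1 uses dosing dates. Second, the phase rule in SAP 5.2 might be meant to govern 5.2.6; sections 5.2.1 to 5.2.4 do not restate it either. Yet 5.2.6 names its own intervals, and the variable list in 5.2 omits concomitant medications, so a programmer would probably follow 5.2.6.

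Finally, an on-drug/off-drug split answers a legitimate safety question: what was given alongside tolvaptan. That stands, and is a reason to keep it as a supplement.

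**Conclusion.** The point holds as a minor gap in a descriptive table. Followed as written, and with the IMP period read as first to last dose, SAP 5.2.6 places 0 of 2 Phase B days in the during column for Early Withdrawal and 2 of 2 for Late Withdrawal subjects who complete dosing. Neither column is like-for-like between arms. The consequence is confined to co-treatment outside rescue therapy and fluid restriction.

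The day count rests on that reading of the IMP period and on scheduled dosing. The percentages are only illustrative: the gap in the during column is about 15 points at an assumed 10% independent daily use (34% − 19%), and zero for a drug continued from Phase A throughout. The plan does not give the use rates or persistence needed to say where a real drug would lie.

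**What to change.** In SAP 5.2.6, define the IMP period by dates and summarize concomitant medications in three windows, in line with SAP 5.2:

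- Phase A: all dosed subjects.
- Phase B: randomization to the end of Phase B, by randomized group, with the same window in both arms whether or not dosing continues; nonresponders shown separately.
- Phase C: follow-up.

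The end of Phase B can be taken from SAP 5.1.7.2. The on-drug/off-drug split can stay as a supplementary table.

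The cost is a wording change and new date windows in one table program. No new data are needed, and nothing in trial conduct changes.

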5.3 Sample Size Re-estimation

It was recommended by the FDA that the sample size should be re-estimated when approximately 90% of the subjects had finished the trial. The sample size re-estimation will assess the variability of change from Day 2 (or 2a) at the end Treatment Phase A to the end of Treatment Phase B in serum sodium level by using the pooled variance of the 2 treatment groups. At the trial planning stage, an SD of 5 was used to detect a treatment difference of 4, resulting in a sample size of 70 with a 2-sided alpha of 0.05 and 90% power. In case the variance ratio (equal to the observed pooled variance divided by 25, the square of 5 as an SD used in the sample size calculation) is ≤ 1 , no sample size increase will be made, and the trial will proceed to finish enrollment of 70 randomized subjects. In case the variance ratio is > 1 , the sample size re-estimation will be equal to 70 multiplied by the variance ratio, then rounded up to the nearest even number.

Table 5.3-1 provides an example of the sample size re-estimation under different variance ratios.

Table 5.3-1 **Sample Size Re-estimation**

Variance Ratio	Sample Size
1.1	78
1.2	84
1.3	92
1.4	78
1.5	106

6 Monitoring of Safety Data

Safety monitoring will be performed by the Independent Data Monitoring Committee (IDMC). Reference is made to the IDMC Charter for details of constituents and roles and responsibilities of IDMC. The independent statistician at Theorem will work closely with the IDMC and will assist the IDMC in the retrieval and analysis of safety and efficacy data. The DMC will review the data periodically. Summary tables will be produced by OPDC (Otsuka Pharmaceutical Development & Commercialization) Biometrics.

7 SAP References

¹ Guidance for Industry, Drug-Induced Liver Injury: Premarketing Clinical Evaluation. US Department of Health and Human Services, Food and Drug Administration, and Center for Drug Evaluation and Research (CDER), July 2009.

Otsuka Pharmaceutical Development & Commercialization, Inc.

This page is a manifestation of an electronically captured signature

OPC-41061

SIGNATURE PAGE

Document Name: P15608276_SAP

Document Number: 0001127440

Document Version: 6.0

Signed by	Meaning of Signature	Server Date (dd-MMM-yyyy HH:mm 'GMT'Z)
[REDACTED]	Clinical Approval	25-Aug-2017 19:06 GMT+00
[REDACTED]	Biostatistics Approval	28-Aug-2017 18:03 GMT+00

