#### **7.4.4 Interim Analysis**

It was recommended by the FDA that the sample size should be re-estimated when approximately 90% of the subjects had finished the trial. The sample size re-estimation will assess the variability of change from Day 2 (or 2a) at the end Treatment Phase A to the end of Treatment Phase B in serum sodium level by using the pooled variance of the 2 treatment groups. At the trial planning stage, an SD of 5 was used to detect a treatment difference of 4, resulting in a sample size of 70 with a 2-sided alpha of 0.05 and 90% power. In case the variance ratio (equal to the observed pooled variance divided by 25, the square of 5 as an SD used in the sample size calculation) is  $\leq 1$ , no sample size increase will be made, and the trial will proceed to finish enrollment of 70 randomized subjects. In case the variance ratio is  $> 1$ , the sample size re-estimation will be equal to

70 multiplied by the variance ratio, then rounded up to the nearest even number. [Table 7.4.4-1](#) provides an example of the sample size re-estimation under different variance ratios.

Table 7.4.4-1      Sample Size Re-estimation	
Variance Ratio	Sample Size
1.1	78
1.2	84
1.3	92
1.4	78
1.5	106

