4.1 Sample Size for Efficacy

A total of 70 randomized subjects will provide 90% power to detect a treatment difference of 4 mEq/L (mmol/L) in change in serum sodium from Day 2 (or 2a) at the end of Treatment Phase A to the end of Treatment Phase B using a 2-sided alpha of 0.05. A standard deviation (SD) of 5 in change of serum sodium was used for the sample size calculation. After the end of Treatment Phase A at Day 2 (or 2a), subjects will be randomized at a ratio of 1:1 to either continue treatment with tolvaptan for 2 additional days (Late Withdrawal) or to discontinue tolvaptan treatment (Early Withdrawal). Sample size re-estimation will be conducted when 90% of the randomized subjects finish (complete or discontinue) the trial.

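### The sample size re-estimation table prints 78 subjects at a variance ratio of 1.4 where the stated rule gives 98; a trial sized from that row would have about 84% power, not 90%

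*SAP*

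**What the plan says.** SAP section 4.1 plans 70 randomized subjects for 90% power to detect a difference of 4 mEq/L in the change in serum sodium, at two-sided 0.05. On variability it says: "A standard deviation (SD) of 5 in change of serum sodium was used for the sample size calculation". Allocation is equal: "subjects will be randomized at a ratio of 1:1".

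SAP section 5.3 and protocol section 7.4.4 then describe a re-estimation when about 90% of subjects have finished. The observed pooled variance is divided by 25 to give a variance ratio. If the ratio is 1 or less, "the trial will proceed to finish enrollment of 70 randomized subjects". If it exceeds 1, the new size is "70 multiplied by the variance ratio, then rounded up to the nearest even number"; the protocol has the same rule ("multiplied by the variance ratio, then rounded up to the nearest even number").

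Each document illustrates the rule in a table (SAP Table 5.3-1, protocol Table 7.4.4-1). The two tables are identical: 78, 84, 92, 78 and 106 at ratios 1.1, 1.2, 1.3, 1.4 and 1.5.

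**The concern.** The required sample size has to rise with the variance. The tabulated sizes rise from 78 to 92, fall back to 78 at ratio 1.4, then jump to 106. The 1.4 entry equals the 1.1 entry and contradicts the rule printed directly above it.

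This is the only planned change to the sample size. It is made late, in an open-label trial, and a prespecified rule should then give one answer. At ratio 1.4 the text gives one number and the table another, 20 subjects apart. Taking the table's number would leave the trial short of the power that the re-estimation exists to protect.

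**Working it through.** **Inputs.** Difference 4 mEq/L, SD 5 (variance 25), two-sided alpha 0.05, power 90%, 1:1 allocation, N = 70 (SAP sections 4.1 and 5.3). No dropout inflation is stated for this calculation.

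**The planned 70.** By the normal approximation, n per arm = 2 × 25 × (1.960 + 1.282)² / 4² = 32.8, so 33 per arm or 66 in total. The two-sample t-test needs 34 per arm (68 in total, power 90.2%). At 35 per arm power is 91.0% (t-test) or 91.7% (normal). The planned 70 for 90% power therefore reproduces, with a small margin.

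**The table.** N = 70 × ratio, rounded up to an even number:

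| Variance ratio | 70 × ratio | Rounded up to even | Printed |
|---|---|---|---|
| 1.1 | 77 | 78 | 78 |
| 1.2 | 84 | 84 | 84 |
| 1.3 | 91 | 92 | 92 |
| 1.4 | 98 | **98** | **78** |
| 1.5 | 105 | 106 | 106 |

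Four rows match. At 1.4 the product is already even, so rounding cannot explain the difference of 98 − 78 = 20 subjects, or 20/98 = 20% of the required size.

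**Could another formula give 78?** At ratio 1.4 the variance is 1.4 × 25 = 35 and the SD is √35 = 5.92. The normal approximation gives 2 × 35 × (1.960 + 1.282)² / 16 = 46.0 per arm, so 92 in total. The t-test needs 94 (power 90.0%). Neither is near 78.

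**Power at ratio 1.4** (difference 4, SD 5.92, two-sided 0.05). The noncentrality is 4 / (5.92 × √(2/n)), with n per arm: 2.99 at n = 39 and 3.35 at n = 49.

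| Total N | Subjects added to 70 | Power, t-test | Power, normal |
|---|---|---|---|
| 70 | 0 | 79.6% | 80.7% |
| 78 (printed) | 8 | 83.8% | 84.7% |
| 98 (rule) | 28 | 91.2% | 91.7% |

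**The case against.** Nobody can defend the cell itself. The case on the other side is that it matters little.

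- The prespecified decision is the worded rule, which is complete and correct, and both documents call the table an example. The variance ratio is continuous and no lookup or interpolation is defined, so almost any observed ratio has to go through the formula. The dip at 1.4 is also easy to notice. This stands: power is lost only if the trial is sized from that row.
- SAP section 5.1 says that enrollment was extremely low, that the trial terminated early, and that efficacy analyses need not go beyond summary statistics. Re-estimation was due at about 63 of 70 randomized subjects (0.9 × 70), so it probably never arose. This also stands as a limit on practical effect. That statement concerns the efficacy analyses, however; it does not mention section 5.3, which remains in the signed SAP.
- The power figures come from an unadjusted two-sample test that takes 1.4 as the true variance ratio, whereas the primary analysis is a repeated-measures model with covariates. This is fair: the figures show the size of the shortfall on the plan's own sizing assumptions and do not predict the power of the model.
- The open-label design does not make the cell a source of bias or of type I error inflation. That is right, and neither is claimed.

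None of this makes 78 consistent with the rule.

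**Conclusion.** The error is real and appears in both current documents. At a variance ratio of 1.4 the rule gives 98 and the tables print 78, which is 20 subjects short. A trial sized from that row would have about 84% power (83.8% by t-test, 84.7% by normal approximation) against the stated 90%; 98 subjects would give 91% to 92%. These figures assume a true difference of 4, a true variance of 35, equal arms, a two-sided 0.05 test and no allowance for dropout or covariate adjustment. That 78 is a typing slip for 98 is likely, but it is an inference. Since the trial stopped early, the consequence now lies mainly in the correctness of the documents. A sample size that contradicts its own rule is nevertheless wrong as written and should be corrected.

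**What to change.** In the row for variance ratio 1.4, replace 78 with 98 in SAP Table 5.3-1 and in protocol Table 7.4.4-1. The rule and the other four rows stay as they are. The cost is one cell in each document, with no effect on design, conduct or analysis method.
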